Mozambique has one of the world's highest HIV/AIDS burdens, and is the home of one of the world's poorest and most medically underserved regions, Zambézia province, located in north-central Mozambique (Fig.1). Adult HIV prevalence in 2009 was 12.6%, but among pregnant women was substantially higher (estimated 20%-28%).[1] According to the 2011 Demographic and Health Survey, 74% of pregnant women in Zambézia attended at least one prenatal visit.[2] In our 2014 unpublished Presidents Emergency Plan for AIDS Relief (PEPFAR) program data, 81% of pregnant woman who came to the antenatal clinic (ANC) were tested for HIV, but only 80% of them initiated antiretroviral therapy (ART). Half of HIV+ pregnant women abandoned care within six months of ART enrollment. Fewer than 40% returned with their infants for Early Infant Diagnosis (EID) services. Among returnees, only 70% of infants received a PCR test to determine HIV status and only 30% of HIV-infected infants were enrolled on ART (unpublished data, FGH-Zambézia). Thus, only 2% of women received all steps of the cascade necessary for PMTCT, probably the lowest program coverage rate in all of sub-Saharan Africa.

In Mozambique, all HIV-infected pregnant women are now eligible for life-long antiretroviral therapy (ART), regardless of CD4+ cell count (Option B+).[3-5] However, retention in care among women enrolled through Option B+ programs remains sub-optimal in sub-Saharan Africa (SSA) [6-8] primarily due to the need for male partner approval to access health services.[9] Poor medication adherence in Option B+ programs increases risk of mother-to-child transmission and ART resistance.[10, 11] In 2012, there were 94,000 HIV-positive pregnant women in Mozambique.[12] PEPFAR implementer, Friends in Global Health data indicated 8.0% of all pregnant women were HIV-positive; 60% had HIV-infected partners in 2014.[9] Eighty percent of HIV-infected pregnant women and <10% of HIV-infected partners identified during antenatal care (ANC) enrolled on ART. Retention was abysmal: 50% of women and 88%

of men abandoned care within six months (FGH M&E data). At one year, 8% of exposed infants in Mozambique were HIV infected vs. only 1.8% in neighboring South Africa.[13, 14]

Role of Male Partners in Retention and Adherence to HIV Health Services

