Question 4: Is the intervention cost-effective? Would the Ministry of Health be willing to scale it up based on our costing data?

7. Study Population

a. Population:

Couples consisting of two adults 18 years or older (one HIV-infected pregnant woman and her HIV-infected male partner) presenting for ANC services together at one of 24 clinical sites in Zambézia province.

b. Inclusion Criteria:

Couples, one HIV+ pregnant woman and her infected male partner, will be eligible to participate if the woman's due date is >2 weeks from enrollment. Both persons must also be 18 years or older, able to give consent, willing to consent to an infant record search, and must agree to enroll in ART together.

c. Exclusion Criteria:

Couples will not be eligible to participate in the study if the woman is not pregnant, if both persons are not HIV+, if either person is younger than 18 years, if one member of the couple is unwilling to enroll in ART or consent to the infant record search, or if one member of the couple is unable to give consent due to mental limitations.

d. Calculations of Sample Size:

Objectives 1 & 3: With 24 clusters and 45 couples per cluster, we have over 80% power to detect a 30% increase in the proportion of pregnant women who initiate ART from 55% to 71.5% with $\alpha = 0.05$. Our power calculations count adults and babies who dropout during the EMTCT cascade (e.g. do not initiate ART) as failures for downstream aims (e.g. retention on ART or viral suppression). For example, SOC ART retention was calculated as the proportion of women who initiated ART multiplied by the proportion of women retained in care ($0.55 \times 0.56 = 0.31$). In our sample size calculation, we power for a 20% increase in adult ART retention (above and beyond the 30% increase in adult ART initiation, for an improvement in retention from 31% to 48%), 90% vs. 80% viral suppression among women or men, 20% increase in EID testing, and 40% reduction in infant HIV positivity. Women, men and infants will be evaluated as separate study populations.

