Objective 2: Aim 2 analyses will utilize a subset of the 1,080 enrolled couples (2,160 individuals) who are alive and can be contacted to provide data by 6 months after enrollment, regardless of whether or not they are retained in care. Because the psycho-social data collected by 6 months may be influenced by whether or not participants were retained through 6 months, our analyses will initially only consider retention outcomes after 6 months to maintain the temporal order needed to infer any mediation effects.

e. Sampling

Participants: HIV infected couples will be enrolled for 6 months at each study site. Patients will be enrolled on a first come, first enrolled basis until 40 couples have been enrolled.

[figure not shown]
f. Patient participant retention and withdrawal:

As per standard clinic procedure, couples on the control arm will receive separate clinical services at the ANC building and the adult HIV clinic, respectively. Peer educators will track all clients who miss appointments at control and intervention sites. The Home Based Care workers will document clients as terminating care if they: (1) discontinued services due to death; (2) transferred their care to another clinic that is not in the study; (3) are lost to follow-up (defined as being >90 days late for a clinic appointment plus 3 failed attempts at tracking the client); or (4) discontinue for any other reason, including patient choice. Clients will not receive any remuneration for participating in the study, per Mozambican National Medical Ethics Committee, but interview participants will be provided a small snack. Clients will be allowed to discontinue participation and may decide that their medical data cannot be used in the analysis at any time during the study.

8. Methods

a. Study Procedures

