For this project, de-identified data will be extracted into a restricted dataset by FGH employees from the existing OpenMRS databases and sent to a VUMC Biostatistician for analysis. All routine programmatic data are owned by the MOH. All routine programmatic data are part of the clinical record and as such will not be destroyed.

Data Analysis

Objective 1: Statistical analysis plan for Objective 1. We propose a generalized linear mixed effects model, with random effect for clinic.[88] A simple model for $E(Y_{ij})$, the probability of ART initiation in the i th clinic at the j th time-point is given by:

$$\text{logit } E(Y_{ij}) = \beta_1 + \beta_2 \text{Group}_{ij} + b_i + e_{ij}$$

where b_i is a random effect for clinic i which accounts for clustering of patients within clinics, due perhaps to similarities in health-seeking behavior and/or access to care. β_1 is a fixed effect

corresponding to time j , $Group_{ij}$ is an indicator of intervention, and β_2 is the treatment effect (difference in log odds of ART receipt). We test the hypothesis, $H_0: \beta_2 = 0$. The mixed effects model will be extended to allow for covariate adjustment, such as: age, education, and distance from clinic. Separate models will be used to assess each outcome in each population (men, women, infants). For example, ART initiation among pregnant women ($n=1,080$) and then ART initiation among male partners ($n=1,080$). All adult patient models will include depression scale scores as covariates in attempts to control for potential presence of depression symptoms among participant groups. Female-specific models allow for inclusion of covariates unique to pregnant women, such as prior ANC, parity, etc. We also expect the intervention odds ratio to differ between women and their male partners. For infant HIV infection, sensitivity analyses will be conducted to investigate the effect of no EID test result on HIV infection; infants of mothers who did not initiate ART or were not retained in care at delivery will be assigned probabilities of infection (with definitions based on latest research). Then, infant HIV status will be multiply imputed using the Bernoulli distribution and estimates from the multiple regressions will be combined with multiple imputation techniques. An intent-to-treat approach will be employed for all analyses.

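### Objective 2 analyses only people who are alive and contactable by 6 months; who is missing is likely to differ by arm, and no missing-data method covers the 6-month scale scores

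*Combined protocol and SAP*

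**What the plan says.** **Analysis set.** Section 7d, Objective 2, states: "Aim 2 analyses will utilize a subset of the 1,080 enrolled couples (2,160 individuals" in number) who are "alive and can be contacted to provide data by 6 months after enrollment, regardless of whether or not they are retained in care". The next sentence concedes that 6-month psychosocial data may be affected by retention. For that reason the mediation work will at first use only retention outcomes after 6 months.

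**Leaving care.** Section 7f gives four routes: death, transfer to a non-study clinic, loss, and any other reason including the patient's choice. Only loss involves failed tracing: clients who "are lost to follow-up (defined as being >90 days late for a clinic appointment plus 3 failed attempts at tracking the client". Peer educators track missed appointments in both arms.

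**Model.** Section 10, Objective 2, reuses the Objective 1 mixed model with a continuous outcome, covariates, and interactions between intervention and baseline score. Mediators associated with the intervention at p<0.20 go into the structural equation model.

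**Missing data.** The only method given is multiple imputation of infant HIV status (Section 10, Objective 1). That paragraph closes with: "An intent-to-treat approach will be employed for all analyses".

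**Contact by arm.** Section 8a gives intervention couples monthly community meetings with an expert peer couple from the first week. It lists no equivalent for control couples.

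**The concern.** Whether a person has a 6-month score depends on being alive and findable after randomisation. Someone who meets the loss definition has already been sought three times without success, and no separate tracing effort for the 6-month interview is described. That person will probably have no score.

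The trial is designed to change retention, and one arm has an additional community contact, so the missing share can be expected to differ between arms. If people who disappear have more stigma, less support or less trust, the arm that loses more of them keeps a more favourable remainder. The comparison then tilts against the arm that holds on to people. The same sample also screens the mediators and feeds the mediation model.

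The investigators accept the general point elsewhere. In Section 8b they prefer published model inputs because programme data suffer from differential loss, with worse outcomes among those lost. The rule of using only retention after 6 months settles temporal order; it does not deal with who is missing.

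**Working it through.** **1. The plan's own figures.** 24 × 45 = 1,080 couples and 2 × 1,080 = 2,160 individuals, as stated. Retention: 0.55 × 0.56 = 0.308 (stated as 31%), and 0.715 × 0.56 × 1.20 = 0.480 (stated as 48%). These reproduce. For Objective 2 the plan gives no power, response rate or subset size to check. (Section 7e stops enrolment at 40 couples, where 7d uses 45 per cluster. If 40 is per site, the base is 24 × 40 = 960 couples. That is a separate point; 45 is used here.)

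**2. How large the analysed set could be.** The background section reports that 50% of women and 88% of men abandoned care within six months. Let q be the share of non-retained people who cannot be contacted. The documents do not give it. Analysed number = 1,080 × (1 − 0.50q) + 1,080 × (1 − 0.88q):

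| q | women | men | total |
|---|---|---|---|
| 0 | 1,080 | 1,080 | 2,160 |
| 0.5 | 810 | 605 | 1,415 |
| 1 | 540 | 130 | 670 |

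These are bounds, because abandonment is not the same as non-contact.

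**3. Bias if there is no true effect.** Inputs:
- Non-retained share, from Section 7d: 1 − 0.31 = 0.69 (control) and 1 − 0.48 = 0.52 (intervention). The time point of these figures is not stated, and they are worked through for women.
- d, the amount by which unreachable people score worse, in SD and the same in both arms. Assumed.
- ICC 0.01 to 0.03. Assumed; the protocol gives none.

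Missing shares: m0 = 0.69q and m1 = 0.52q. Each observed arm mean is too favourable by d × m, so bias against the intervention = d × (m0 − m1) = d × 0.17q.

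SE² = sum over arms of [1 + (45(1 − m) − 1) × ICC] / [12 × 45(1 − m)], ignoring the matching.

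Rejection = P(Z > 1.96 − bias/SE) + P(Z < −1.96 − bias/SE).

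For q = 0.5, d = 0.5, ICC 0.01:
- m0 = 0.345 and m1 = 0.26, so 29.475 and 33.3 people are observed per clinic.
- SE² = 1.28475/353.7 + 1.323/399.6 = 0.00694, so SE = 0.083.
- Bias = 0.5 × 0.085 = 0.0425, and bias/SE = 0.51.
- Rejection = 0.0735 + 0.0068 = 8.0%.

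| q | d | bias (SD) | SE, ICC 0.01 / 0.03 | two-sided rejection, ICC 0.01 / 0.03 |
|---|---|---|---|---|
| 0.5 | 0.2 | 0.017 | 0.083 / 0.101 | 5.5% / 5.3% |
| 0.5 | 0.5 | 0.043 | 0.083 / 0.101 | 8.0% / 7.1% |
| 0.5 | 0.8 | 0.068 | 0.083 / 0.101 | 12.9% / 10.4% |
| 1 | 0.2 | 0.034 | 0.107 / 0.121 | 6.2% / 5.9% |
| 1 | 0.5 | 0.085 | 0.107 / 0.121 | 12.5% / 10.9% |
| 1 | 0.8 | 0.136 | 0.107 / 0.121 | 24.7% / 20.4% |

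The nominal rate is 5%.

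**The case against.** Four stronger readings are tempting, and the documents do not support them.

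- *The phrase about retention is false.* A reader might infer that the sample is claimed to be independent of retention and that the claim fails. The text says only that retention is not a condition of inclusion, and the following sentence acknowledges that retention may influence the data. Transfers, people who stop by choice, and people who are late but traced are not retained and can still be interviewed.
- *Lost simply means uncontactable.* The definition also needs more than 90 days' lateness. By 6 months it can therefore catch only people whose missed appointment fell in about the first three months. It is a care-termination code, and nothing equates clinic tracking with the attempt to reach someone for the survey.
- *Intent-to-treat is broken.* The restriction is disclosed, and nothing suggests that anyone is analysed outside the assigned arm. The shortfall is missing outcomes.
- *50% and 88% are the missing fractions.* They are programme abandonment figures, not non-contact rates, and do not come from couples who agreed to start ART together. A gap such as 50% against 30% missing would give 0.10 SD and 16–20% rejection at d = 0.5, but no document states it, and its 20 points exceed the 17-point gap in planned retention.

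Three further points are fair. Tracking covers both arms. The model adjusts for age, education, depression scores and distance and uses baseline scores in interactions, so d should be read as the difference left after adjustment. The assumed bias runs against the intervention, so a false finding of benefit becomes rarer (under 1% at q = 0.5, d = 0.5, against a nominal 2.5%).

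These points reduce the size and certainty of the problem. They do not supply a missing-data method, and adjustment for baseline variables does not handle loss driven by later events.

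**Conclusion.** The point stands in limited form. Objective 2 is an available-case analysis with likely differential non-response and no plan for it. At d = 0.5 SD and ICC 0.01–0.03, the bias against the intervention is about 0.04 SD (7–8% rejection) if half of the non-retained are unreachable, and 0.085 SD (11–13%) if all are. With d between 0.2 and 0.8 the effect runs from negligible to material.

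The result depends on d, the ICC, the unreachable share, and the use of planned retention as a guide to the arm difference; only the last comes from the protocol. The direction depends on unreachable people scoring worse, by a similar amount in each arm. The change is worth making because it is cheap and the mechanism results are hard to interpret without it. The documents do not show that Objective 2 is invalid.

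**What to change.** Amend Section 10, Objective 2, as follows.

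1. Take as the analysis population all enrolled adults alive at 6 months who have not withdrawn their data. Section 7f allows withdrawal, and scores should not be imputed for people who have died.
2. Multiply impute missing 6-month scores by arm and sex, allowing for clinic. Use baseline scores, baseline PHQ-9, the partner's scores, and 6-month care status with its reason (retained, transferred, lost, stopped for another reason) as imputation variables only.
3. Few clients classed as lost will have observed scores, so imputation alone will say little about them. Pre-specify a delta-shift sensitivity analysis for this group, with the range of shifts fixed in advance.
4. Report the contacted-only analysis alongside, and state that it is not full intent-to-treat.
5. Report response by arm, sex and care status, and define what counts as contactable and how many interview attempts are made.

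The cost is SAP text and some analysis time. The protocol already plans to collect the baseline scales, PHQ-9 and reasons for leaving care. The downside is that intervals will rest on stated missing-data assumptions.

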This study is important because it targets the health and well-being of the mother-infant-male partner triad,^[50] the essential family group that has eluded effective engagement strategies in HIV care. It builds on our research team's extensive experience in: (1) HIV care and treatment; (2) male partner engagement; (3) and cost-effectiveness analysis. Our results will improve outcomes by effectively engaging couples in HIV care and treatment during pregnancy and beyond. Without effective innovation in culturally appropriate adherence support to all stages of the care continuum, EMTCT efforts will fail in rural Africa.

6. Design and Study Questions

We propose to conduct a matched-pair cluster Randomized Controlled Trial to evaluate the effects of our intervention. To our knowledge, this is the first ANC-based couples study that will assess definitive treatment outcomes within a randomized controlled trial (RCT), and analyze the cost-effectiveness of the intervention. Twenty-four primary and secondary level health care facilities in Zambézia Province will be matched and then randomized to the control (standard-of-care [SOC]) or intervention (HoPS+) arms (12 sites per arm). We opted for a study design in which the unit of randomization is the EMTCT clinic (not the individual) because it would be extremely difficult to implement the intervention to only a subset of clients within each facility. We will match clinics on ART uptake rates, retention in care among patients on treatment, patient volume, HIV prevalence in ANC, and level of facility (secondary or primary)^[51] using reweighted Mahalanobis distances^[52] and then randomize clinics in each matched pair to intervention and SOC arms – 12 clinics per arm, 24 total. Intervention and control sites will be >100 km of each other to prevent contamination.

There are four specific study questions:

Question 1: Is our intervention idea (partners-based ART services for expectant and post-partum couples) acceptable to expectant couples?

Question 2: Does our intervention positively impact partner support for ART medication adherence and retention in care? Does it increase empathy among partners enrolled? Does it increase knowledge about HIV? Does it reduce HIV stigma among couples enrolled into the intervention?

Question 3: Does our intervention improve the proportion of exposed infants who are tested for HIV (early infant diagnosis)? Does it decrease the number of infants who are HIV-positive at 12 months?

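### Power and the analysis populations assume 45 couples per clinic (1,080), but the enrolment rule stops at 40 per clinic (at most 960)

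*Combined protocol and SAP*

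**What the plan says.** The combined protocol and SAP gives the sample size in four places.

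- **Section 7d (Calculations of Sample Size), Objectives 1 and 3:** "With 24 clusters and 45 couples per cluster, we have over 80% power to detect a 30% increase" in ART initiation among pregnant women, from 55% to 71.5% at alpha 0.05. On dropout, the section says: "Our power calculations count adults and babies who dropout during the EMTCT cascade" as failures for the later steps.
- **Section 7d, Objective 2:** the analyses use "a subset of the 1,080 enrolled couples (2,160 individuals") who are alive and can be reached by 6 months.
- **Section 10 (Data Analysis, Objective 1):** the separate models for women and for men are each given n = 1,080.
- **Section 7e (Sampling):** "HIV infected couples will be enrolled for 6 months at each study site", followed by: "Patients will be enrolled on a first come, first enrolled basis until 40 couples have been enrolled".

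Section 6 fixes the design at 24 clinics, matched and randomized within pairs, 12 per arm.

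**The concern.** Three statements depend on 45 couples per clinic, while the sentence that tells sites when to stop enrolling says 40. If sites follow section 7e, the trial cannot reach the number behind its power statement or the populations named in its analysis section. The final report would show an apparent 11% recruitment shortfall even though every site had met its written target. If sites instead aim for 45, they enrol past the written stop. The plan states no ICC, so a reader also cannot confirm from the documents that the power claim survives at 40.

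**Working it through.** **1. The plan's own totals.** 24 clinics × 45 couples = 1,080 couples, and 2 × 1,080 = 2,160 adults. Both agree with section 7d, and the 1,080 agrees with section 10.

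**2. The totals under section 7e.** The stop at 40 is read per site because the preceding sentence refers to each study site. A trial-wide limit of 40 would mean 40 / 24 = 1.7 couples per clinic.

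| | Section 7d (45 per clinic) | Section 7e (40 per clinic) | Difference |
|---|---|---|---|
| Couples | 24 × 45 = 1,080 | 24 × 40 = 960 | 120 (120 / 1,080 = 11.1%) |
| Couples per arm | 12 × 45 = 540 | 12 × 40 = 480 | 60 |
| Adults | 2,160 | 1,920 | 240 |

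**3. Could 45 be 40 plus an allowance for losses?** No. The 1,080 couples are called enrolled, and dropouts stay in the denominator as failures. An allowance would also put the larger number in the enrolment rule, whereas here the enrolment rule has the smaller one.

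**4. Effect on power.** Inputs from the plan are 12 clinics per arm, alpha 0.05 (taken as two-sided), initiation 55% vs 71.5%, and retention 31% vs 48%. The ICC is an assumption and is shown over a range.

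- Effective number per arm: n = 12m / (1 + (m − 1) × ICC), where m is couples per clinic. At ICC 0.05 this is 540 / (1 + 44 × 0.05) = 540 / 3.2 = 168.8 for m = 45, and 480 / (1 + 39 × 0.05) = 480 / 2.95 = 162.7 for m = 40.
- Normal approximation: power = Φ{ (|p2 − p1|√n − 1.96√(2p̄(1 − p̄))) / √(p1(1 − p1) + p2(1 − p2)) }, where p̄ is the mean of p1 and p2.
- Initiation at ICC 0.05: p̄ = 0.6325, 1.96 × √0.4649 = 1.336, and √(0.2475 + 0.2038) = 0.672. For m = 45, (0.165 × √168.8 − 1.336) / 0.672 = 1.20, so power is 88.5%. For m = 40, (0.165 × √162.7 − 1.336) / 0.672 = 1.14, so power is 87.4%.
- Small-sample version: noncentral t with noncentrality |p2 − p1| / √((p1(1 − p1) + p2(1 − p2)) / n). It is shown with 22 df (24 clinics, matching ignored) and 11 df (12 matched pairs, no variance gain from matching). This version uses the unpooled variance, so it differs from the normal figures by slightly more than the degrees of freedom.

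Power at 45 → 40 per clinic:

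| Outcome | Assumed ICC | Normal | t, 22 df | t, 11 df |
|---|---|---|---|---|
| Initiation | 0.03 | 96.1% → 95.2% | 94.7% → 93.7% | 92.6% → 91.3% |
| Initiation | 0.05 | 88.5% → 87.4% | 86.2% → 84.9% | 82.7% → 81.4% |
| Initiation | 0.07 | 79.9% → 78.7% | 77.1% → 75.9% | 73.0% → 71.8% |
| Retention | 0.03 | 96.6% → 95.8% | 95.3% → 94.4% | 93.3% → 92.1% |
| Retention | 0.05 | 89.5% → 88.4% | 87.3% → 86.1% | 83.9% → 82.6% |
| Retention | 0.07 | 81.1% → 80.0% | 78.4% → 77.3% | 74.4% → 73.2% |

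The loss from 45 to 40 is about 1 point in every row. Differences down the table come from the assumed ICC, not from the 45/40 conflict. For initiation, the largest ICC that keeps 80% power (normal approximation) falls from 0.070 to 0.067. If the ICC were such that 45 per clinic gave exactly 80%, 40 per clinic would give 78.9%.

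**5. Viral suppression.** For 80% vs 90%, taken as plain proportions, the loss is at most 1.8 points (normal approximation, ICC 0 to 0.20).

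**The case against.** The best defence is that this is a slip of five couples in one sentence. Every other count agrees on 45 or 1,080, so a stale or mistyped number in section 7e is at least as likely as a real plan to enrol fewer. The sentence does not itself say per site, a figure next to section 7e is not shown and might clarify it, and the power loss is minor. The 11-df column is also harsher than the analysis described, since the section 10 model has a random effect for clinic and no term for the matched pair.

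Much of this is fair, but it bears on weight rather than substance. A typing error is plausible, though the documents cannot settle which number is intended, and the stopping sentence is the one that governs enrolment at the sites. Per site is the natural reading, and the trial-wide reading makes the conflict far worse. Whatever the figure shows, the written rule would still contradict the written total. Nothing readable presents 40 as a minimum or lets one clinic make up for another. Section 7e also sets a 6-month window, so 40 is not the only limit on enrolment. The window can only lower the total, and 960 remains the ceiling. Dropping the 11-df column changes nothing, because the loss is about 1 point with any of the three methods.

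**Conclusion.** The point holds. As written, enrolment can reach at most 960 couples, not the 1,080 used for power and named as the analysis populations: 120 couples, 240 adults, or 11.1% fewer. This rests on reading the stop at 40 as per site and as a cap.

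The statistical cost is small. It is about 1 point of power for initiation and retention across the assumed ICCs, because with 24 clinics the clustering matters more than five couples per clinic. The conflict does not by itself show that the claim of more than 80% power fails; without a stated ICC the documents can neither confirm nor refute that claim at either number. The small loss was not shown for early infant diagnosis or infant HIV positivity, for which section 7d gives relative changes without baseline rates. This is a certain inconsistency with a modest effect, and it should be corrected.

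**What to change.** Use one per-site number in the section 7d power statement, the section 7d Objective 2 population, section 7e, and the Objective 1 analysis in section 10. State in section 7e that the number applies to each site.

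- **If 40 is kept:** restate 960 couples, 1,920 adults, and n = 960 women and n = 960 men, then recompute power at 40 per clinic and name the ICC used. The cost is wording and one recalculation, with power about 1 point lower for initiation and retention.
- **If 45 is kept:** change the stop in section 7e to 45. This is the smaller edit, but it means up to 5 more couples per clinic (120 in all), and the sponsor should confirm that 45 can be reached within the 6-month window.

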Objective 2: Individuals consented in the study will complete interviewer-assisted, quantitative study measures at baseline and by 6 months post-study enrollment, including measures of: 1) partner social support;[45] (2) HIV stigma;[46] (3) empathy [47]; (4) HIV knowledge;[48] and (5) patient trust in provider.[49]

Objective 3: Clinical outcomes of the linked models include MTCT risk at birth and weaning, pediatric life expectancy from birth, maternal and paternal life expectancy from presentation to care, and combined (maternal + paternal + pediatric) life expectancy. Economic outcomes, from the healthcare system perspective, include antenatal and postnatal program costs, lifetime maternal HIV-related healthcare costs, lifetime pediatric healthcare costs, and 1 to 5-year maternal and pediatric health care costs. We will use these outcomes to calculate incremental cost-effectiveness ratios (ICERs) in \$/life-year (LY) as the difference in combined healthcare costs (program + maternal lifetime + paternal lifetime + pediatric lifetime costs) between the two strategies, divided by the difference in combined projected life expectancy (maternal + paternal + pediatric life expectancy). For ICERs, all outcomes will be discounted at 3%/year.[79-81] We will consider a strategy to be "cost-saving" if it leads to greater combined life expectancy and lower combined costs than an alternative strategy. Following WHO guidance and evolving consensus in the field of cost-effectiveness analysis, we will consider a strategy to be "cost-effective," compared to its alternative, if its ICER is <0.5-1.0x Mozambique *per-capita* gross domestic product (GDP: \$525 in 2015)/LY. Recognizing the limitations of this approach, we will also compare ICERs to other HIV interventions in Africa, e.g., first line ART (\$500-\$5,500/LY).[82-86]

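### The cost-effectiveness rule in 8b puts no condition on the sign of the ICER's parts, so as written it gives the reverse of the right verdict whenever HoPS+ yields fewer life-years

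*Combined protocol and SAP*

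**What the plan says.** Section 6 asks, as Question 4, "Is the intervention cost-effective", and goes on to ask whether the Ministry of Health would scale the programme up on the costing data.

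Section 8b (Measurement of Results, Objective 3) gives the working definitions. The numerator of the ICER is defined "as the difference in combined healthcare costs (program + maternal lifetime + paternal lifetime + pediatric lifetime costs) between the two strategies", and this is "divided by the difference in combined projected life expectancy (maternal + paternal + pediatric life expectancy". The plan adds: "For ICERs, all outcomes will be discounted at 3%/year".

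Two labels follow:

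- A strategy is 'cost-saving' "if it leads to greater combined life expectancy and lower combined costs than an alternative strategy". This label states a direction for both differences.
- For the second label, "we will consider a strategy to be 'cost-effective,' compared to its alternative, if its ICER is <0.5-1.0x Mozambique" per-capita GDP, given as USD 525. This label states no direction for either difference.

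As a secondary yardstick, "we will also compare ICERs to other HIV interventions in Africa, e.g., first line ART", with a range of USD 500 to 5,500 per life-year.

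The cost-effectiveness text in 8a and the Objective 3 analysis text in section 10 describe the models and cost inputs. Neither mentions dominance, net benefit or what to do when life expectancy is lower with HoPS+.

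**The concern.** A ratio does not keep the signs of its parts. A negative ICER can mean cheaper and better or dearer and worse. A small positive ICER can mean a cheap gain or a small saving bought with a large loss of life-years. A rule that looks only at whether the ratio lies below a positive threshold cannot separate these cases.

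A negative life-expectancy difference is possible here. Section 8b feeds the trial's cascade proportions by arm into the MTCT model, and section 10 describes that model as deterministic. Chance differences between arms can therefore carry through to the sign of the life-expectancy difference, and no uncertainty criterion is attached to the threshold rule. HoPS+ also adds six counselling sessions and about nine peer-couple sessions (8a), so a higher programme cost is the natural expectation. What is at stake is the pre-specified answer to Question 4, which the plan links to scale-up.

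**Working it through.** **Inputs.** From 8b: the ICER definition and the GDP figure of USD 525. The threshold T therefore runs from 0.5 x 525 = 262.50 to 1.0 x 525 = 525 USD per life-year. The plan states no incremental cost, life-year gain or error rate for this rule, so there is no figure of its own to reproduce. The cost and life-year pairs below are illustrations chosen to show signs, not forecasts.

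**Notation.** dC is the difference in combined costs and dLE the difference in combined life expectancy, HoPS+ minus standard of care (SOC). The written rule passes if dC/dLE < T. Incremental net monetary benefit is NMB = T x dLE - dC.

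**Algebra.**

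- If dLE > 0, multiplying dC/dLE < T by dLE gives dC < T x dLE, that is NMB > 0. The written rule is correct.
- If dLE < 0, the multiplication reverses the inequality: dC > T x dLE, that is NMB < 0. The written rule passes exactly when net benefit is negative.
- If dLE = 0, the ratio is undefined and the rule gives no answer.

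None of this depends on T, on the cost level or on any error distribution.

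**Numbers.**

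| dC (USD) | dLE (LY) | ICER (USD/LY) | Written rule at 262.50 / 525 | NMB at 262.50 / 525 |
|---|---|---|---|---|
| +100 | +0.4 | 250 | pass / pass | +5 / +110 |
| +100 | +0.2 | 500 | fail / pass | -47.50 / +5 |
| -100 | +0.1 | -1,000 | pass / pass | +126.25 / +152.50 |
| +100 | -0.1 | -1,000 | pass / pass | -126.25 / -152.50 |
| -100 | -1.0 | 100 | pass / pass | -162.50 / -425 |
| -100 | -0.1 | 1,000 | fail / fail | +73.75 / +47.50 |

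The first three rows have more life-years, and rule and net benefit agree. The last three have fewer, and they disagree every time. The third and fourth rows have the same ICER and opposite meanings.

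**Symmetry.** Swapping the two strategies changes both signs: (-dC)/(-dLE) = dC/dLE. In the first row, HoPS+ against SOC is 250 per life-year and so is SOC against HoPS+, so each is 'cost-effective' compared with the other. Likewise, when HoPS+ meets the 'cost-saving' definition, SOC has the same negative ICER and passes the threshold rule.

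**Can a frequency be attached?** Suppose dLE is normal about zero with standard deviation s (no effect), and dC = P + k x dLE, with P the programme cost and k the downstream cost per life-year. For P > 0 and k > 0, the chance of a dearer and less effective result is Phi(P/(k x s)) - 0.5. All three inputs are assumptions:

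- k = 0: 50%, the ceiling.
- P = 50, k = 250, s = 0.467: 50/(250 x 0.467) = 0.428, giving about 17%.
- P = 50, k = 1,000, s = 0.467: 50/(1,000 x 0.467) = 0.107, giving about 4%.

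The answer is set almost wholly by inputs that the documents do not give.

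**The case against.** The best defence is that no health economist would apply the sentence literally. The plan introduces it as following WHO guidance and consensus in the field, and then acknowledges the limits of a threshold. By convention a dearer, less effective option is reported as dominated. Life expectancy and costs are listed as outcomes in their own right, so a loss of life-years would be visible beside any ICER. Question 4 also treats the Ministry's willingness to scale up as a separate matter, so the label triggers nothing automatically.

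Much of this stands, and it makes a wrong published verdict less likely. It does not repair the rule. The plan did write down directions for 'cost-saving', so its silence on direction for 'cost-effective' cannot be put down to a general habit of leaving them implicit. A pre-specified rule should not need an unwritten override once results are known.

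A reader might infer something stronger: that under no effect HoPS+ would be called cost-effective while dearer and less effective about half the time or more. The documents do not support that. With error symmetric about zero, that outcome cannot exceed 50%, and it can be far lower. The numerator includes lifetime care costs of mother, father and child, which can fall when life-years fall, so a positive programme cost does not guarantee a positive total. The plan's only cost-per-life-year comparator, USD 500 to 5,500 for first-line ART, suggests that downstream cost may lie near or above the threshold, where the rate drops. Nor can the noise be taken from infant infections in the trial: 8b draws MTCT risks from published data, and the denominator includes both parents.

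**Conclusion.** Wrong as written. The inversion follows from the two definitions in 8b alone and holds at both ends of the threshold band and for a point estimate. It affects every result with fewer combined life-years, and the identical verdict for HoPS+ and SOC affects every result with a defined ratio. Verdicts on HoPS+ with more life-years are correct.

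How often the faulty region would be reached is unknown. It depends on programme cost, downstream cost per life-year and sampling error, none of which the documents state, so no frequency should be claimed. The conclusion assumes only that the sentence is applied as it reads; an analyst following convention would avoid the error, but the plan does not tell them to.

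**What to change.** In 8b, replace the threshold sentence with a rule of this kind: HoPS+ is cost-effective compared with SOC if T x (difference in combined life expectancy) minus (difference in combined costs) is greater than zero, at the stated threshold T. If the 0.5 to 1.0 band is kept, give the verdict at each end.

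Add that HoPS+ is labelled dominated, and not cost-effective, when it costs more and combined life expectancy is equal or lower. A cheaper, less effective result is judged by the same net-benefit rule.

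If the ICER wording is preferred, apply 'ICER < T' only when combined life expectancy is higher with HoPS+. The two forms agree there; results with equal or lower life expectancy still need the net-benefit rule and the dominance label.

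The cost is one or two sentences, using the same model outputs, with no new data or participants. No correct verdict with more life-years changes.
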